8.2.5 Prognostic factor analyses

Except for the analyses described in the previous sub-section, there are no other prognostic factor analyses foreseen in the current protocol.

8.2.6 Data recoding and display

Frequency tables will be tabulated (by treatment group or otherwise) for all categorical variables by the levels of the variables as they appear on the CRF (with %). Categories with a text field specification will be tabulated as categories and then supplemented by a listing with the following information for the patients fulfilling the condition for the specification (patient id, institution, treatment group, value of the item and text field contents).

Dates relating to events prior to entry will be presented as the delay in days (or weeks, months, or years) between the past event and the date of entry (date of randomization – date of past event + 1) and presented using the median and range. For example, on the randomization checklist, the date of last administration of prior treatment (or the date of first diagnosis of the cancer) will be presented as the time elapsed (in days, weeks, months or years, as appropriate) since the day of the last administration and the date of entry on study (date of randomization – last administration/diagnosis +1).

Other delays (e.g. re-treatment delays) are presented as continuous variables using the median and range.

Continuous variables for which a coding system exists (such as for laboratory data) will be recoded into categories (for adverse events, the grading scale specified in the protocol will be used). Whenever no specific scale exists, lab data will be categorized based on the normal range: for example, below the lower normal limit (when appropriate), within the normal range, above the upper normal limit (ULN) and the degree to which it is above the ULN (for example > 2.5 x ULN, > 5 x ULN, > 10 x ULN). For laboratory data, the nadir is generally displayed. The nadir in a given visit is the lowest laboratory value in that cycle; the overall nadir for a patient is the lowest laboratory value among all cycles.

Other continuous variables (for example age, dose ...) are presented using the median and range (minimum, maximum).

$$\text{DI observed} \left[\frac{\text{mg}}{\text{m}^2 \times \text{weeks}} \right] = \frac{\text{total dose} \left[\frac{\text{mg}}{\text{m}^2} \right]}{\text{total duration} [\text{weeks}]}$$

The relative dose intensity is calculated as the ratio of the dose intensity as calculated above to the dose intensity indicated in the protocol. The dose intensity indicated in the protocol is obtained as the dose specified per visit (in mg/m²).

The dose intensity and the relative dose intensity are presented using median and ranges. The relative dose intensity can also be presented in categories ($\leq 70\%$, >70-90%, >90-110%, >110-120%, >120).

If appropriate, continuous data may also be presented in categories (for example, age may also be grouped in decades).

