7.2.2 General evaluation of adverse events

This study will use the International Common Terminology Criteria for Adverse Events (CTCAE), version 4.03, for adverse event reporting. A copy of the CTCAE can be accessed from the EORTC home page <https://www.eortc.be/services/doc/ctc/>.

Hematological toxicity will be assessed on the basis of regular blood tests. The nadir count will be computed at each study medication administration and graded according to the CTCAE version 4.03.

Non hematological acute side effects will be assessed and reported separately for each study medication administration, and graded according to the CTCAE version 4.03.

Planned safety analysis and tabulations are described in the statistics Chapter 8.

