8.2.3.2 Toxicity

Analysis for toxicity is based on the safety population. The worst grade of toxicity/adverse events observed over the whole treatment period according to CTCAE version 4.03 will be displayed. In the primary analysis, no formal statistical analysis will be performed to compare toxicity between arms.

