- ◆ is life-threatening (i.e. an event in which the subject was at risk of death at the time of event; it does not refer to an event which hypothetically might have caused death if it was more severe)
- ◆ requires inpatient hospitalization or prolongation of existing patient hospitalization
- ◆ results in persistent or significant disability or incapacity
- ◆ is a congenital anomaly or birth defect
- ◆ is a medically important event or reaction.
- ◆ Medical and scientific judgment should be exercised in deciding whether other situations should be considered serious such as important medical events that might not be immediately life-threatening or result in death or hospitalization but might jeopardize the patient or might require intervention to prevent one of the other outcomes listed in the definition above. Examples of such events are intensive treatment in an emergency room or at home for allergic bronchospasm, blood dyscrasias or convulsions that do not result in hospitalization, or development of drug dependency or drug abuse.

ECI: Selected serious and nonserious AEs are also known as Event of Clinical Interests (ECIs) and must be reported to the Sponsor. Events of clinical interest for this study include:

- ◆ Drug Induced Liver Injury (DILI): AST or ALT elevations ≥ 3 x ULN with concurrent elevation of total bilirubin ≥ 2 x ULN and, at the same time, alkaline phosphatase < 2 x ULN
- ◆ If grade \geq Grade 2: Nephritis, Autoimmune nephritis, Renal Failure, Acute Renal Failure, Acute interstitial pneumonitis, Interstitial lung disease, Pneumonitis
- ◆ If grade \geq Grade 2 or any grade resulting in dose modification (please refer to [Appendix H](#)) or use of systemic steroids to treat the AE: Intestinal Obstruction, Colitis, Colitis microscopic, Necrotizing colitis, Enterocolitis, Hemorrhagic enterocolitis, GI perforation, Diarrhea, Hepatitis, Autoimmune hepatitis, Transaminase elevations, Uveitis, Iritis
- ◆ If grade \geq Grade 3 or \geq Grade 2 and resulting in dose modification (please refer to [Appendix H](#)) or use of systemic steroids to treat the AE: Adrenal Insufficiency, Hyperthyroidism, Hypothyroidism, Thyroid Disorder, Thyroiditis, Hypophysitis, Hypopituitarism

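### Section 8.2.6 makes the lowest value the general display for all laboratory tests, the wrong direction for AST, ALT, bilirubin, creatinine and glucose, whose toxicity in this protocol is an elevation

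*Combined protocol and SAP*

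**What the plan says.** Section 8.2.6 (Data recoding and display) first sets a recoding rule: "Continuous variables for which a coding system exists (such as for laboratory data) will be recoded into categories", with the protocol's grading scale used for adverse events. Where no specific scale exists, laboratory values are to be classed against the normal range, including "the degree to which it is above the ULN (for example > 2.5 x ULN, > 5 x ULN, > 10 x ULN".

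It then chooses the value to show: "For laboratory data, the nadir is generally displayed". The nadir is defined per visit as the lowest value in the cycle, and per patient: "the overall nadir for a patient is the lowest laboratory value among all cycles". The section names no peak or maximum, and it exempts no test.

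Two other sections bear on this. Section 7.2.2 uses the nadir only for blood counts: "Hematological toxicity will be assessed on the basis of regular blood tests. The nadir count will be computed at each study medication administration". Section 8.2.3.2 gives the main toxicity display: "The worst grade of toxicity/adverse events observed over the whole treatment period according to CTCAE version 4.03 will be displayed".

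**The concern.** For neutrophils, platelets or hemoglobin, low is the adverse direction and the nadir is the right summary. For several chemistry tests the protocol defines harm the other way:

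- Section 16.1 lists "Drug Induced Liver Injury (DILI): AST or ALT elevations" together with raised bilirubin as an event of clinical interest, and also lists transaminase and creatinine elevations.
- Appendix G grades hepatic events by multiples of ULN or baseline, and nephritis by increased creatinine.
- Appendix G also tracks Grade 3 or 4 hyperglycemia with evidence of beta-cell failure.

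For these tests a per-patient lowest value reports the best result each patient had. Safety is a secondary objective (Section 2.2). Laboratory tables are useful because they show measured abnormalities by arm without depending on whether an investigator judged the value to be an event. A table of lowest values cannot do that for elevations.

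**Working it through.** The plan gives no figure on this point to reproduce. The check is a reading of the text plus one illustration.

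**Step 1. Which value is displayed.** For a patient with values x1, ..., xm in multiples of ULN, the rule displays min(x). The toxicity of interest for AST, ALT, bilirubin, creatinine and glucose is governed by max(x).

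**Step 2. One patient.** Inputs: 18 infusions (Section 5.4), chemistry before each (Section 6.3.1), and the Appendix G cut-points for AST/ALT with a normal baseline (Grade 2 above 3 to 5, Grade 3 above 5 to 20, Grade 4 above 20 x ULN). Assumed ALT values: 15 at 0.6 x ULN and one excursion of 8, 3.5 and 1.4 x ULN.

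- min = 0.6 x ULN: within normal limits, no grade.
- max = 8 x ULN: Grade 3.

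If the only raised value is 1.4 x ULN, min is still 0.6 and max is 1.4. That rise is below the Grade 2 cut-point, so it is not an event of clinical interest unless the dose was modified or systemic steroids were given. It is the kind of value that only a laboratory table would show.

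**Step 3. How often an elevation survives the rule.** A patient's nadir is above ULN only if every value is. Suppose, purely for illustration, that each of m = 18 values is independently above ULN with probability p:

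- P(at least one value raised) = 1 - (1 - p)^18
- P(nadir raised) = p^18

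| p | at least one raised | nadir raised |
|---|---|---|
| 0.05 | 0.603 | <0.001 |
| 0.20 | 0.982 | <0.001 |
| 0.50 | >0.999 | <0.001 |
| 0.80 | >0.999 | 0.018 |

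Arms with p = 0.05 and p = 0.20 would differ as 0.603 against 0.982 on the maximum, and both would be below 0.001 on the nadir. Values within a patient are correlated in practice, which narrows the gap, but a transient rise is lost whatever the correlation. Dropping the sample before infusion 1 (m = 17) changes little: 1 - 0.95^17 = 0.582 and 0.8^17 = 0.023.

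**Step 4. Consistency with the rest of the plan.** For tests left to the ULN categories, a lowest value reaches an above-ULN class only when the patient is never below it, so those classes have little use under the nadir rule. For tests with a CTCAE scale on the high side, grading the lowest value returns the mildest grade, while Section 8.2.3.2 calls for the worst.

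**The case against.** The case for leaving the text alone has real force on four points.

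- **The rule is hedged.** The word *generally* makes the nadir a default. That stands, but no exception is named, so the direction of the summary is left to whoever programs the tables.
- **A worst-grade display is already planned, and reporting is mandatory.** An abnormal laboratory finding can be an adverse event (Section 16.1), and all adverse events up to 30 days after treatment must be reported (Section 16.6). Transaminase elevations of Grade 2 or higher, DILI, creatinine elevations of Grade 3 or higher, and Grade 3 or higher hyperglycemia with ketosis or acidosis are events of clinical interest. The ALT of 8 x ULN above would therefore be reported and shown. A reader might infer that elevations disappear from the safety results, but the documents do not support that. What remains exposed is the rest: lower-grade creatinine rises, hyperglycemia without ketosis or acidosis, Grade 1 transaminase rises, and isolated bilirubin, ALP or LDH rises, none of which is a listed event of clinical interest by grade alone.
- **The ULN categories are a fallback.** A reader might infer from Table 3, which requires AST/ALT at or below 2.5 x ULN before treatment, that the categories above 2.5 x ULN must be empty in both arms. That does not follow. Those categories apply only where no specific scale exists, and AST/ALT have graded cut-points in Appendix G. The argument also needs the pre-treatment sample to count as a cycle value. Section 8.2.6 does not say so, and Table 4 lists that sample apart from the treatment period.
- **TSH is different.** A reader might add raised TSH to the list of toxicities. The protocol uses it as a trigger for T3 and T4 testing, not as a graded toxicity, and because hyperthyroidism is also tracked, a low value can matter too.

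**Conclusion.** The point holds as a defect in a stated rule, of moderate size. As written, Section 8.2.6 selects the wrong extreme for AST, ALT, bilirubin, creatinine and glucose, and it conflicts with its own above-ULN categories, with Section 8.2.3.2 and with the narrower use in Section 7.2.2. Transient elevations would drop out of the per-patient laboratory tables.

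The practical loss is mainly measured elevations, largely lower-grade, that were not recorded as adverse events. Its size cannot be computed from the documents, because it depends on how completely sites report laboratory findings as events. The probabilities above rest on assumed, independent values and show direction only. Section 8.2.3.2 plans no formal comparison of toxicity between arms, so what is at stake is description.

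**What to change.** In Section 8.2.6, replace the nadir rule with text to this effect:

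> For each laboratory test, the worst on-treatment value in the direction of toxicity is displayed, per cycle and overall. The lowest value (nadir) is used for blood counts and other tests where low is adverse; the highest for AST, ALT, bilirubin, ALP, LDH and creatinine; both the lowest and the highest for two-directional tests such as TSH, glucose, sodium, potassium and calcium. Results are summarised by arm as worst CTCAE grade where a scale exists and by the ULN categories otherwise.

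The text should also say that the sample before infusion 1 is baseline and not an on-treatment value. Shift-from-baseline tables would be a useful option but are not needed to repair the defect.

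The cost is protocol/SAP wording and table programming. Chemistry is already collected every 3 weeks and TSH every 6 weeks (Sections 6.3.1 and 6.3.2), so there is no new data collection.

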KN001 D, KN002, KN010 and KN021), and three studies compared 10 mg/kg Q3W vs 10 mg/kg Q2W (KN001 B3, KN001 F2 and KN006). All of these studies demonstrated flat dose- and exposure-response relationships across the doses studied representing an approximate 5 to 7.5 fold difference in exposure. The 2 mg/kg (or 200 mg fixed-dose) Q3W provided similar responses to the highest doses studied. Subsequently, flat dose/exposure-response relationships were also observed in other tumor types including head and neck cancer, bladder cancer, gastric cancer and classical Hodgkin Lymphoma, confirming 200 mg Q3W as the appropriate dose independent of the tumor type. These findings are consistent with the mechanism of action of pembrolizumab, which acts by interaction with immune cells, and not via direct binding to cancer cells. Additionally, pharmacology data clearly show target saturation at 200 mg Q3W. First, PK data in KN001 evaluating target-mediated drug disposition (TMDD) conclusively demonstrated saturation of PD-1 in systemic circulation at doses much lower than 200 mg Q3W. Secondly, a PBPK analysis was conducted to predict tumor PD-1 saturation over a wide range of tumor penetration and PD-1 expression. This evaluation concluded that pembrolizumab at 200 mg Q3W achieves full PD-1 saturation in both blood and tumor. Finally, population PK analysis of pembrolizumab, which characterized the influence of body weight and other subject covariates on exposure, has shown that the fixed-dosing provides similar control of PK variability as weight based dosing, with considerable overlap in the distribution of exposures from the 200 mg Q3W fixed dose and 2 mg/kg Q3W dose. Supported by these PK characteristics, and given that fixed-dose has advantages of reduced dosing complexity and reduced potential of dosing errors, the 200 mg Q3W fixed-dose was selected for evaluation across all pembrolizumab protocols.

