5.4 Treatment schedule

Pembrolizumab/Placebo at a dose of 200 mg, administered intravenously (IV), every 3 weeks, for a total of 18 infusions, approximately one year.

Note: if visits are missed and/or delayed treatment will continue beyond 1 year in order to complete 18 infusions.

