6.3 During treatment

Pregnancy test: serum (or urine) beta HCG in fertile female study participants. This pregnancy test is to be renewed/repeated during protocol treatment at least monthly or more frequently if required by national regulations/institution guidelines.

Infusion schedule

1) Normal schedule

Window of administration is up to 3 days before or after the scheduled day of each infusion, due to administrative reasons, except for infusion 1 where the window is + 7 days from randomization.

2) Delayed infusions

Definition of **delayed** infusion: an infusion is considered as delayed if administration occurs at least 3 days after the theoretical date, but less than 10 days after the theoretical date. Future infusion dates should follow every 3 weeks, calculated from the actual date of administration of the delayed infusion. If **infusion is delayed** (e.g. patient on holiday, adverse events, hospitalized, etc) the site must:

- ◆ Complete all protocol required laboratory tests, physical exam, adverse events assessments, concomitant medication assessments and HRQoL assessments within the required window prior to the new date of infusion.
- ◆ Follow calendar days for imaging assessment and not adjust for delays. The reference date for imaging scans must be the date of the first infusion (infusion 1).

3) Missed infusions

Definition of **missed** infusions: an infusion is considered as missed if administration would occur more than 10 days after the theoretical date. In this case, no infusion is given. The next infusion should occur as soon as the cause of the missed infusion is resolved and not delayed until the next scheduled infusion. Future infusion dates should follow every 3 weeks, calculated from the actual date of administration of the delayed infusion.

If **infusion administration is missed** (e.g. toxicity, delay greater than 10 days, etc), the site must:

[figure not shown]
- ◆ Complete all protocol required laboratory tests, physical exam, adverse events assessments, concomitant medication assessments and HRQoL assessments within the required window prior to the **missed** date of infusion administration. If a visit did not occur, documentation is required (see CRF completion guidelines).
- ◆ Follow calendar days for imaging assessment and do not adjust for delays. The reference date for imaging scans must be the date of the first infusion (infusion 1).

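### Relative dose intensity in Section 8.2.6 divides a dose per week by a dose per visit, so full on-schedule treatment computes to about 33–35% instead of about 100%

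*Combined protocol and SAP*

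**What the plan says.** Section 8.2.6 (Data recoding and display) prints a formula for observed dose intensity: total dose in mg/m² over total duration in weeks, with the result in mg per m² per week. It then gives two rules:

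- For the ratio: "The relative dose intensity is calculated as the ratio of the dose intensity as calculated above to the dose intensity indicated in the protocol".
- For its denominator, with mg/m² as the unit: "The dose intensity indicated in the protocol is obtained as the dose specified per visit".

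On reporting, it says "The dose intensity and the relative dose intensity are presented using median and ranges". It adds that "The relative dose intensity can also be presented in categories", with cut-offs at 70, 90, 110 and 120%.

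The treatment itself is set out in Section 5.4: "Pembrolizumab/Placebo at a dose of 200 mg, administered intravenously (IV), every 3 weeks, for a total of 18 infusions". Section 5.2.1 confirms that the dose does not scale with body size: "the 200 mg Q3W fixed-dose was selected for evaluation across all pembrolizumab protocols". The overdose definition in Section 16.1 agrees, since it equates 1000 mg with five times the dose.

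**The concern.** The two terms of the ratio are on different time scales. The numerator is per week; the denominator is per visit, and visits are three weeks apart. The ratio therefore carries the unit 1/week and is not a percentage. It understates relative dose intensity by a factor of 3 for every patient.

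The unit mg/m² is a separate slip. With a fixed 200 mg dose there is no protocol dose per square metre to put in the denominator.

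The median and range of relative dose intensity are planned without condition. Followed literally, the rule would show a reader a median near one third in a trial where delivery was complete. The optional categories presuppose that full delivery lies near 100%, so they would separate almost no one. Infusion counts would not fill the gap: Section 5.5 lets treatment run beyond a year to reach 18 infusions, so a count alone does not show delay.

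**Working it through.** The documents state no relative dose intensity (RDI) value, so there is no figure to reproduce. The check applies the rule as written and then applies it with matching units.

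**Inputs**

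- Dose 200 mg, interval 3 weeks, 18 infusions (Section 5.4). Total: 18 × 200 = 3600 mg.
- Total duration: start and end are not defined in the visible text. Assumed range: 51 weeks (first to last infusion, 17 × 3) to 54 weeks (18 full intervals, 18 × 3).
- Infusion window (Section 6.3): "Window of administration is up to 3 days before or after the scheduled day of each infusion".
- Category cut-offs 70, 90, 110 and 120% (Section 8.2.6).

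**Formulas**, for n infusions over w weeks

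- As written: RDI = (n × 200 / w) / 200 = n / w.
- Same time unit in both terms: RDI = (n × 200 / w) / (200 / 3) = 3n / w.

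The second is always three times the first, whatever the duration convention.

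| Case | Observed, mg/week | As written | Consistent units |
|---|---|---|---|
| 18 infusions, 54 weeks | 66.67 | 33.3% | 100.0% |
| 18 infusions, 52 weeks | 69.23 | 34.6% | 103.8% |
| 18 infusions, 51 weeks | 70.59 | 35.3% | 105.9% |
| 18 infusions, 60 weeks (delays) | 60.00 | 30.0% | 90.0% |
| 9 infusions, 54 weeks (half the dose) | 33.33 | 16.7% | 50.0% |

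**Effect on the categories.** True values of 70, 90, 110 and 120% become 70/3 = 23.3, 90/3 = 30.0, 110/3 = 36.7 and 120/3 = 40.0%, all in the lowest category. To exceed 70% as written, the true value must exceed 3 × 70 = 210%. Even 18 infusions all given 18 days apart reach only 38.9% (18 intervals counted) or 41.2% (17 intervals counted).

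**Very short exposure.** Counting duration from first to last infusion with a gap of g days, the value as written is 7n / ((n − 1)g).

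- n = 2: g = 18 gives 77.8%, g = 19 gives 73.7%, g = 20 gives 70.0%, g = 21 gives 66.7%.
- n = 3: g = 18 gives 58.3%.

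Under this count, only patients with exactly two infusions 18 or 19 days apart leave the lowest category, and a single infusion has no value because the duration is zero.

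**Role of mg/m².** If both terms are divided by the same body surface area, it cancels and 33.3–35.3% stands. If only the numerator were converted and 200 kept below, an assumed body surface area of 1.6 to 2.0 m² (the documents give none) would yield 16.7–22.1%. The factor of 3 comes only from the missing interval.

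**The case against.** The strongest reply is that the intended quantity is easy to recover. The comparator is called a dose intensity, the formula just above gives that term per week, the schedule is in Section 5.4, and the categories sit around 100%. A programmer would probably see the slip as soon as almost every patient landed in the lowest category. This is fair, and the wrong figures would appear only if the rule were followed literally. But a silent repair would be an undocumented departure from the plan, and it would leave the duration rule to whoever makes it.

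It can also be said that the measure is merely descriptive. That stands, and it limits the weight of the point: relative dose intensity is not an endpoint, the toxicity analysis in Section 8.2.3.2 does not use it, a constant factor preserves the ordering of patients and arms, and the categories are optional.

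The mg/m² formula might have been meant for adjuvant chemotherapy. The denominator rules this out. Section 3.3.2 leaves chemotherapy to national and local guidelines, so the protocol specifies no chemotherapy dose per visit.

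Text may have been lost in reading the PDF, since the formula has no introduction. This weakens any complaint that "total duration" is undefined. It does not rescue the denominator, whose defining sentence is complete and shows no redaction.

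Finally, the short-exposure figures depend on conventions. Section 8.2.6 adds one day when it counts delays before entry. If duration were counted that way, two infusions 19 days apart would give 14/20 = 70.0%, and a single infusion would be defined and very high (7/1 = 700%). If the calendar is not re-anchored after an early second infusion, the earliest third infusion is day 39, and the value is 21/39 = 53.8% rather than 58.3%. These figures are therefore conditional; the main result does not rest on them.

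**Conclusion.** The concern holds. As written, relative dose intensity is one third of its proper value for every patient. Eighteen on-schedule infusions compute to 33.3% (54 weeks) or 35.3% (51 weeks), against 100% and 105.9% with matching units. Apart from a few patients with very short exposure, everyone would fall in the category of 70% or less. No other section corrects the denominator, and the category above 90 to 110% shows that full delivery was meant to sit near 100%.

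The factor of 3 needs only the 3-week interval in Section 5.4. The exact percentages also rest on the assumed 51 to 54 weeks. The consequence is a misleading exposure table, not a threat to any efficacy or toxicity conclusion. It is worth correcting because a stated rule gives a wrong reported number and the correction is almost free.

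**What to change.** Rewrite the definition in Section 8.2.6 so that both terms are in mg/week:

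- Observed dose intensity = total mg administered / total weeks.
- Protocol dose intensity = protocol dose per infusion / protocol interval, which from Section 5.4 is 200 mg / 3 weeks = 66.7 mg/week.
- Relative dose intensity = observed / protocol.

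Remove mg/m². State how total duration is counted. Any stated convention will do, and for completers it moves the corrected value only between 100% and 105.9%. It matters for short exposure: two on-schedule infusions give (400/3)/66.7 = 200% counted first to last, but (400/6)/66.7 = 100% if one interval is added after the last infusion. A first-to-last rule also needs a provision for patients with one infusion.

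Name the source of the milligrams administered. The treatment-form variables visible in Appendix N are an administration date and a yes/no flag, but they are listed there only to derive the last date known alive, so the form may hold more. Section 5.3.4 places the amounts given in the drug accountability records.

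The cost is a change of wording in one section, assuming the milligrams given can be derived. It alters an analysis definition only; the dose and schedule are untouched.
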